### 5.6.2 All-cause mortality

Vital status will be assessed at the LFU visit, whether performed in person or by telephone contact.

### 5.6.3 Microbiological outcome

The microbiological outcome categories at EOT and TOC are defined below. For a patient to have a favorable microbiological response, the outcome for each baseline pathogen must be eradicated or presumed eradicated. If the outcome for any pathogen is persistence or presumed persistence, the patient will be considered to have an unfavorable microbiological response.

Microbiological outcome is to be assessed at the EOT and TOC visits by the Investigator as follows

- ***Eradication***: Absence of baseline pathogen in follow-up cultures of source specimen
- ***Presumed eradication***: Absence of follow-up microbiological evaluation of source specimen, or unavailable microbiological results, for a patient with a valid baseline pathogen who was assessed as a clinical cure
- ***Persistence***: Continued presence of a baseline pathogen in follow-up cultures of any source specimen
- ***Presumed persistence***: Absence of follow-up microbiological evaluation of source specimen or unavailable microbiological results for a patient with a valid baseline pathogen and assessed as a clinical failure
- ***Unevaluable***: No valid pathogen identified at baseline, or no follow-up microbiological evaluation of source specimen obtained in a patient with clinical outcome assessed as unevaluable
- ***Relapse***: Baseline pathogen detected again in follow-up microbiological evaluation of any source specimen obtained between the TOC and LFU visits after documented eradication or presumed eradication at the TOC visit (note: this applies only to the microbiological outcome assessment at the LFU visit)

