### 5.2.4 Test-of-cure visit

The following assessments and procedures will be performed at the TOC visit (7–14 days after the last dose of study drug; see Table 3):

- Physical examination (see Section 5.5.2)
- Body weight (see Section 5.5.2)
- Vital signs (including body temperature, respiratory rate, pulse rate, and systolic and diastolic blood pressures) and pulse oximetry (see Section 5.5.3)

- Signs and symptoms of LOS (see Section 5.6.5)
- Local laboratory tests will be performed only if clinically indicated based on the Investigator's judgement in accordance with local standard of care (see Section 5.5.4)
- Imaging tests (e.g., chest X-ray, ultrasound, CT scan, MRI) will be performed if clinically indicated based on the Investigator's judgement in accordance with local standard of care.
- Collection of blood and other specimens for microbiological evaluation as clinically indicated based on the Investigator's judgement in accordance with local standard of care (see Section 5.4).
- Overall clinical outcome assessment: clinical cure, clinical failure, or unevaluable (see Section 5.6.1)
- Microbiological outcome assessment: eradication, presumed eradication, persistence, presumed persistence, or unevaluable (see Section 5.6.3)
- Review and recording of changes in concomitant medications and concomitant procedures
- Adverse events must be monitored and recorded as outlined in Section 7.4.

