### 5.4 Microbiology assessments

Microbiological evaluation and outcome assessment may be based on blood samples, urine, cerebrospinal fluid, or any other suitable specimen samples.

If clinically indicated and performed as part of the patient's regular medical care, blood is to be obtained for microbiological evaluation at the Screening visit/Baseline (if possible before any antibiotics are administered), or at any time through to LFU visit. Cultures should be repeated in accordance with standard of care if a positive result is obtained, until sterilization is confirmed. Gram stain, culture/PCR, and organism identification are to be performed at the local or regional laboratory, as applicable. All isolates, regardless of specimen source, are to be sent to the central microbiology laboratory for final organism identification and study-specific susceptibility testing.

See the Laboratory Manual for procedures regarding the collection, processing, storage, and shipment of pathogens. Rules for the assessment of the validity of pathogens are described in the Statistical Analysis Plan (SAP).

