### 4.2.2 Clinically Evaluable population

The Clinically Evaluable (CE) population consists of patients in the ITT population who received at least 48 hours of study drug and had a completed overall clinical outcome assessment at the TOC visit, no major protocol deviations, and no concomitant systemic non-study antibiotic therapy.

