### 4.2.3 Microbiological Intent-to-treat population

The mITT population consists of all patients in the ITT population with a causative pathogen identified at baseline.

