### 8.3 Microbiological response

Microbiological outcome is to be assessed at the EOT and TOC visits by the Investigator as ‘Eradication’, ‘Presumed eradication’, ‘Persistence’, ‘Presumed persistence’, ‘Unevaluable’, or ‘Relapse’ (see protocol Section 5.6.3 for details). If applicable, the relapse status of the patient is to be assessed at the LFU visit, by the Investigator.

Patients will be considered to have experienced microbiological eradication if they are classified as ‘Eradication’ or ‘Presumed eradication’. Microbiological eradication at EOT and TOC, and relapse status at the LFU visit, will be summarized in a table for the mITT and ME populations.

All microbiological data will be listed.

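### In mITT, a negative culture taken under rescue antibiotics can count as eradication for an infant who failed ceftobiprole and had no follow-up culture before the switch

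*Protocol*

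**What the plan says.** Protocol 5.6.3 defines Eradication as "Absence of baseline pathogen in follow-up cultures of source specimen". Clinical outcome enters the classification only when follow-up microbiology is missing. One such category, Presumed persistence, covers absent follow-up or "unavailable microbiological results for a patient with a valid baseline pathogen and assessed as a clinical failure".

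SAP 8.3 sets the responder rule: "Patients will be considered to have experienced microbiological eradication if they are classified as" Eradication or Presumed eradication. On reporting it says: "Microbiological eradication at EOT and TOC, and relapse status at the LFU visit, will be summarized in a table", for the mITT and ME populations.

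The two populations treat rescue differently. CE requires "no major protocol deviations, and no concomitant systemic non-study antibiotic therapy" (SAP 4.2.2), and ME is a subset of CE. SAP 4.2.3 sets no such condition: "The mITT population consists of all patients in the ITT population with a causative pathogen identified at baseline".

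Protocol 5.6.1 makes clinical failure, apart from death attributable to late-onset sepsis (LOS), a stop of study treatment with a need for non-study antibacterials, because of insufficient effect or a related adverse event.

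On sampling, protocol 5.4 states: "Cultures should be repeated in accordance with standard of care if a positive result is obtained, until sterilization is confirmed". At TOC the protocol provides for "Collection of blood and other specimens for microbiological evaluation as clinically indicated" (5.2.4), so a culture there is not mandatory.

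**The concern.** Eradication in mITT is a listed secondary endpoint of a single-arm trial, so a reader will take the rate as a description of what the study regimen achieved. Consider an infant with a confirmed baseline pathogen who fails ceftobiprole, is switched to a non-study systemic antibacterial for LOS, and has no follow-up culture of the source specimen before the switch. If a later culture under the rescue drug is negative, the text allows Eradication, and SAP 8.3 tabulates a success. Without that culture, and with a clinical failure rating at the visit, the infant is Presumed persistence. Ceftobiprole did the same thing in both cases; the only difference is whether someone took a culture after the rescue drug was started.

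At stake is the attribution of one infant's clearance in a very small denominator. If the infant is a non-success at EOT and a success at TOC, the rise between the two columns could also be misread as late clearance by ceftobiprole.

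**Working it through.** The plan gives no figure for this rate, so there is nothing to reproduce. The check has four steps.

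**1. Classification under protocol 5.6.3**, for an infant with a valid baseline pathogen. The culture column is the follow-up source-specimen evidence available at the visit.

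| Culture | Clinical cure | Clinical failure | Clinically unevaluable |
|---|---|---|---|
| Negative | Eradication | Eradication | Eradication |
| Positive | Persistence | Persistence | Persistence |
| None | Presumed eradication | Presumed persistence | Unevaluable |

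In the failure column, a negative culture changes the infant from non-success to success. In the unevaluable column (for example, under 48 hours of study treatment) it does the same, because under the SAP 4 denominator Unevaluable also counts against the rate.

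**2. Is there another rule that catches the case?**
- The clinical Unevaluable item on other antibacterials (protocol 5.6.1) covers drugs given for reasons other than LOS, so rescue for LOS falls outside it.
- Protocol 8.4.5 and SAP 4.3.4 deal with missing data, not with an observed negative culture.
- No text carries an EOT failure forward to TOC. Protocol 4.4 asks that discontinued infants complete EOT and LFU and does not name TOC, so a TOC failure rating is not assured.
- The Investigator assigns the category and might discount a culture taken under rescue, but nothing requires it.

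**3. When can it happen?**
- TOC is 7–14 days after the last dose, which is 168–336 hours. At the half-life of about 3.5 hours in protocol 3.3.4, that is 168/3.5 = 48 to 336/3.5 = 96 half-lives. If the half-life were 7 hours (an assumption), it would be 24 to 48. A culture taken at TOC is not taken under ceftobiprole.
- EOT may be held up to 24 hours after the last dose (protocol 5.2.3). If rescue starts and a culture is taken inside that window, the infant can be Eradication at EOT as well.

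**4. Size.** With all mITT patients in the denominator (SAP 4), one infant shifts the rate by 100/n percentage points. The mITT size is not stated. Protocol 4.6 closes each group at its minimum (two term, six pre-term), which gives at most about 8. It may be fewer, because presumed LOS without a pathogen is eligible (protocol 4.2). I assume n = 2 to 8.

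| n | Shift (points) | Infant a non-success, all others eradicated | Infant counted as Eradication |
|---|---|---|---|
| 8 | 12.5 | 7/8 = 87.5% | 100% |
| 6 | 16.7 | 5/6 = 83.3% | 100% |
| 4 | 25.0 | 3/4 = 75.0% | 100% |
| 2 | 50.0 | 1/2 = 50.0% | 100% |

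With one other infant also not eradicated, n = 6 gives 5/6 = 83.3% instead of 4/6 = 66.7%. Exact (Clopper–Pearson) 95% intervals at n = 6 are 35.9–99.6% for 5/6 and 54.1–100% for 6/6. They overlap widely.

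**The case against.** **An observed result should outrank a presumption.** The presumed categories exist only for absent or unavailable results, so using a real culture when there is one is coherent. This stands. A reader might infer that the plan contradicts itself; it does not. The problem is narrower: under rescue, the observed result describes another drug's effect.

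**mITT is meant to keep every infant with a pathogen, and ME already gives a rescue-free rate.** It is true that ME is unaffected. But this is not only a preference between estimands. The plan's own clinical outcome counts a switch for lack of effect or a related adverse event as failure, including in ITT, so crediting the same switch as microbiological success in mITT sits badly beside it.

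**No rate here isolates ceftobiprole.** Ampicillin and aminoglycosides are permitted alongside it (protocol 5.3.3), and the proposed rule leaves them alone. This stands as a limit: the rate describes the study regimen, and an infant who clears on continued ampicillin or an aminoglycoside after ceftobiprole stops would still be a success.

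**The case needs several things at once, and it is visible elsewhere.** Both parts largely stand. Repeat culturing under protocol 5.4 should leave few failing infants uncultured before a switch, although that instruction is not confined to time on ceftobiprole and can itself produce the negative culture under rescue. The ITT clinical outcome table gives reasons for failure, and the listings show the cultures and the drugs. A reader might infer that the EOT column always exposes the case as well; it does so only if no post-switch culture was taken by EOT.

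**The remedy is asymmetric.** It sets aside negative cultures after the switch and keeps positive ones. That is deliberate, since a pathogen still growing under a further drug has not been eradicated. The cost is real, however: an infant switched for a related adverse event would become Presumed persistence without evidence of persistence.

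**Conclusion.** The point holds as a minor one. In mITT, protocol 5.6.3 and SAP 8.3 together allow clearance under a rescue drug to be tabulated as eradication for an infant who failed ceftobiprole and had no follow-up source culture before the switch. This arises mainly at TOC, and at EOT only within the 24-hour window.

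One such infant is worth 1/n: 12.5 points at n = 8, 16.7 at n = 6 and 25.0 at n = 4. These figures assume the SAP 4 denominator and an mITT of at most about eight.

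A reader might infer that the mITT rate will be inflated, or that the trial's conclusions are affected. The documents support neither. They give no frequency for the case, the rate is secondary and descriptive, no hypothesis is tested, the primary objective is safety, and ME is unaffected. Nor is every negative TOC culture in a failed infant suspect: if a source culture before the switch was already negative, Eradication is properly earned.

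**What to change.** Add to SAP 8.3, and note in SAP 12:

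> For the mITT eradication rates at EOT and TOC, negative cultures collected after the start of non-study systemic antibacterial therapy for LOS (other than ampicillin or an aminoglycoside) are treated as not available. For each baseline pathogen, the last follow-up source culture before that therapy decides Eradication or Persistence. If there is none, clinical failure (including failure at EOT, carried forward to TOC) gives Presumed persistence, and a clinically unevaluable infant is Unevaluable. A positive culture of the baseline pathogen after the switch remains Persistence. The Investigator's category is kept in the listing, and reclassified infants are footnoted.

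The rule must cover both visits; otherwise one post-switch culture could give Eradication at EOT and Presumed persistence at TOC. The derived category replaces the Investigator's in this table only.

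The cost is one paragraph and one line before database lock. Concomitant medications and microbiology are already recorded, and patient care does not change. Protocol section 8 asks for an amendment only when a principal feature is altered, and a derivation rule for a secondary descriptive rate should not be one.

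The downside is that the rate may be slightly lower, and an infant whom ceftobiprole did clear but who was not cultured before the switch, including one switched for a related adverse event, would not count as a success.

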#### **5.6.4 Relapse at LFU**

At the LFU visit, the Investigator must assess relapse as follows:

- Deterioration of the patient's clinical condition compared to the TOC visit, microbiological recurrence, or the requirement for additional antimicrobial therapy for LOS

#### **5.6.5 Signs and symptoms of LOS**

The Investigator must rate the following signs and symptoms of LOS as:

- 'absent' or 'present' at baseline (pre-dose)
- 'absent', 'improved', 'unchanged' or 'worsened' compared to baseline, on every day of active study treatment, and at the EOT, TOC, and LFU visits

1. Fever ( $> 38.0^{\circ}\text{C} / 100.4^{\circ}\text{F}$  rectal;  $> 37.5^{\circ}\text{C} / 99.5^{\circ}\text{F}$  axillary;  $> 37.5^{\circ}\text{C} / 99.5^{\circ}\text{F}$  oral;  $> 38.0^{\circ}\text{C} / 100.4^{\circ}\text{F}$  tympanic)
2. Hypothermia ( $< 36.6^{\circ}\text{C} / 97.9^{\circ}\text{F}$  rectal;  $< 36.5^{\circ}\text{C} / 97.7^{\circ}\text{F}$  axillary;  $< 35.5^{\circ}\text{C} / 95.9^{\circ}\text{F}$  oral;  $< 35.8^{\circ}\text{C} / 96.4^{\circ}\text{F}$  tympanic)
3. Abnormal heart rate
  - a. Bradycardia ( $< 100$  beats/minute awake;  $< 80$  beats/minute asleep)
  - b. Tachycardia ( $> 205$  beats/minute awake;  $> 160$  beats/minute asleep)
4. Signs of impaired circulation
  - a. Urine output  $0.5\text{--}1$  mL/kg/h (in patients with urinary catheters; note: urinary catheters are not required for the purposes of this study)
  - b. Hypotension
  - c. Signs of impaired peripheral perfusion, such as mottled skin, moist and cold skin, finger to forearm temperature gradient, or increased capillary refill time
5. Petechial rash OR sclerema neonatorum
6. Respiratory distress
  - a. New onset or worsening of apnea episodes
  - b. Tachypnea episodes
  - c. Increased oxygen requirements
  - d. Requirement for ventilatory support (note: proven ventilator-associated pneumonia is an exclusion criterion; see Section 4.3)
7. Gastrointestinal distress
  - a. Feeding intolerance
  - b. Poor sucking
  - c. Abdominal distension
8. Irritability
9. Lethargy
10. Muscular hypotonia

#### **5.7 Pharmacokinetic assessments**

PK will be assessed by means of sparse blood sampling on Day 3: pre-dose and at 2 hours (end of infusion), 4 hours, and 8 hours, as described in detail in the Laboratory Manual. PK samples should not be taken from the infusion lines.

## 6 STUDY TREATMENT

### 6.1 Blinding

This is an open-label study.

### 6.2 Randomization

This is a single-arm study. At least two term (gestational age  $\geq$  37 weeks) and six pre-term (gestational age  $\geq$  24 to 36 weeks) neonates and infants, with post-natal age ranging from  $\geq$  3 days to  $\leq$  3 months will be enrolled, with no stratification.

### 6.3 Packaging and labelling

The study drug will be packed and labelled in accordance with local regulations and the Annex 13 Good Manufacturing Practice rules. Labels will include the identity of the Sponsor and Investigator, protocol number, drug identification, storage conditions, content of study drug, and expiry date. Information on drug shipment including temperature logger and acknowledgement of receipt form to be completed by the receiver will also be included.

### 6.4 Shipping and storage conditions

Vials of sterile lyophilised ceftobiprole medocaril containing the equivalent of 500 mg ceftobiprole will be shipped to the study sites, and the dry powder must be stored in a refrigerator (2–8 °C / 36–46 °F). All study drug must be kept under secure conditions, e.g., in the hospital pharmacy.

Further information on the shipping and storage conditions is provided in the Pharmacy Manual.

### 6.5 Preparation, presentation, and stability of study drug

Details on the presentation, preparation (including reconstitution and dilution steps), and stability of study drug are provided in the Pharmacy Manual.

### 6.6 Dosage and administration of study drug

Eligible patients will receive ceftobiprole as a 2-hour IV infusion according to the schedule in [Table 5](#), with dose adjusted according to gestational and post-natal ages. Body weight on Day 1 should be obtained within 12 hours prior to the first dose of study drug. From Day 2 until the last day of study treatment, the dose should be calculated based on the patient's first body weight of the day.

**Table 5 Ceftobiprole dosing regimen for the treatment of neonates and infants with LOS**

Gestational age group (weeks)	Post-natal age (days)			
	3 – 13	14 – 29	30 – 59	60 – 90
24 – 26	7.5 mg/kg q12h	7.5 mg/kg q12h	10 mg/kg q12h	10 mg/kg q12h
27 – 31	10 mg/kg q12h	10 mg/kg q12h	10 mg/kg q12h	15 mg/kg q12h*
32 – 36	10 mg/kg q12h	10 mg/kg q12h	15 mg/kg q12h*	15 mg/kg q12h*
≥ 37	15 mg/kg q12h*	15 mg/kg q12h*	15 mg/kg q12h*	15 mg/kg q8h*

Note: All doses will be infused over 2 hours. The maximum allowable dose in adult and pediatric patients is 500 mg regardless of body weight.

\* Neonates and infants with a body weight < 4 kg should receive a maximum of 10 mg/kg/dose.

If ampicillin and/or an aminoglycoside are added, these IV solutions must not be mixed with ceftobiprole or administered through the same line as ceftobiprole. For further details, see the Pharmacy Manual.

## 6.7 Compliance and drug-supply accountability

The Investigator, and a pharmacist or a pharmacist delegate assigned by the Investigator, must maintain records of the delivery of study drug to the site, the inventory at the site, the use by each patient, and the return to the Sponsor or alternative disposal of unused product.

A Drug Dispensing Log must be kept current and must contain the following information:

- Identification of the patient to whom the drug was dispensed
- Principal Investigator name
- Dates, quantity and batch number of the drug dispensed to the patient
- Quantity of the drug remaining

The inventory must be available for inspection by the Sponsor's monitor(s). All supplies, including partially used or empty vials, must be available for checking by the Sponsor's monitor(s) during monitoring visits and at the end of the study.

### 6.7.1 Drug disposal

Any remaining drug, including empty vials, may be returned to the study supply packaging provider, or may be destroyed at the site on the request of the Sponsor provided the drug destruction is adequately documented.

## 7 SAFETY

The role of the DSMB in ensuring the protection of patients' safety is described in Section 3.4.

Stopping criteria for individual patients are described in Section 4.4.

### 7.1 Warnings and precautions

#### 7.1.1 Ceftobiprole

Detailed warnings and precautions related to ceftobiprole are provided in the IB.

Serious and occasionally fatal adverse reactions have been reported in patients receiving beta-lactam antibiotics, including hypersensitivity (anaphylaxis) and *Clostridioides difficile*-associated colitis or pseudomembranous colitis. Seizures have been associated with the use of ceftobiprole, most commonly occurring in patients with pre-existing central nervous system/seizure disorders. Precipitation can occur when ceftobiprole medocaril is mixed with calcium-containing solutions in the same IV administration line. Therefore, ceftobiprole medocaril and calcium-containing solutions, except Lactated Ringer's solution for injection, must not be mixed or administered simultaneously in the same intravenous line.

#### 7.1.2 Ampicillin / aminoglycosides

The safety profiles of these standard-of-care antibiotics that may be combined with ceftobiprole at the discretion of the Investigator are well characterised due to their use over many years, and are described in their respective local labels.

Serious or significant adverse reactions that may occur in patients receiving ampicillin include hypersensitivity (anaphylaxis) and *Clostridioides difficile*-associated colitis or pseudomembranous colitis. Concurrent administration of ampicillin and allopurinol increases substantially the incidence of skin rashes.

Aminoglycosides generally have a narrow therapeutic window and therapeutic drug monitoring should be considered in patients treated with aminoglycosides to ensure adequate therapeutic exposure and to avoid toxicity due to overexposure. Relevant adverse reactions include among others hypersensitivity, ototoxicity, nephrotoxicity, impaired neuromuscular transmission, convulsions, and *Clostridioides difficile*-associated colitis or pseudomembranous colitis.

If ampicillin and/or an aminoglycoside are added, these IV solutions must not be mixed with ceftobiprole or administered through the same line as ceftobiprole.

